2.2.2 Randomization and Blinding

Patients who meet all inclusion criteria and no exclusion criteria will be randomized 1:1:1 to Ziltivekimab 15 mg, Ziltivekimab 30 mg, or matching placebo (12 patients per group) for a 12-week Treatment Period. Approximately 36 patients will be randomized. Patient randomization will be stratified by CKD stage. CKD stage is stratified into two categories: (1) stage 3 and (2) stages 4 and 5.

This study is double-blind. The patients, Investigators, site personnel, site monitors, Sponsor, and contract research organization (CRO) clinical operational personnel will be blinded to the treatment assignment. Ziltivekimab and matching placebo will be provided as a liquid for subcutaneous injection.

The randomization list will be generated by an independent CRO statistician not otherwise involved in the study.

In case of a medical emergency or medical situation in which the treatment assignment is necessary for proper patient management, the Investigator may obtain the treatment assignment from the IWRS. The Investigator should make every reasonable attempt to contact the Medical Monitor before unblinding a patient. In all cases, the Investigator must submit a written report, including all pertinent details, to the Medical Monitor within 24 hours of the unblinding.

2.2.3 Study Drug

Ziltivekimab is supplied as a liquid for injection. Drug product is presented as a single use vial and any unused portion must be discarded.

The Ziltivekimab doses to be tested in this study are 15 and 30 mg per injection. Patients will receive subcutaneous injections of either their assigned dose of Ziltivekimab or matching placebo during the study.

Study drug is planned to be administered every 28 days for a total of 3 treatments on Day1, Weeks 4 and 8. The total cumulative dosage will be 45 mg for those patients randomized to 15 mg per injection, and 90 mg for those patients randomized to 30 mg.

2.2.4 Sample Size Determination

The primary efficacy endpoint is the difference in the mean percent change in hs-CRP from Baseline to the End of Treatment (average of Week 10 and Week 12) between each active group and placebo. Based on the observed treatment difference of -60.74% between combined COR-001-01 active and placebo and the associated pooled SD of 16.893% in hs-CRP at Week 4 from the final analysis of study COR001-SC1, a sample size of 6 patients per group provides 90% power with 2-sided $\alpha = 0.05$. Therefore, the planned sample size of 12 patients per group (total of 36 patients) will provide sufficient power for the study.

2.3 Study Endpoints

2.3.1 Primary Efficacy Endpoints

The primary PD endpoint is the difference in the percent change in hs-CRP levels from Baseline (average of all hs-CRP values prior to the administration of study drug) to the End of Treatment (average of Week 10 and Week 12) between each active group and placebo.

2.3.2 Exploratory Efficacy Endpoints

The exploratory efficacy endpoints include the following:

- Difference in the proportion of patients achieving hs-CRP response, defined as hs-CRP < 2.0 mg/L, at End of Treatment (average of Week 10 and Week 12) between each active group and placebo.
- Difference in the percent change in fibrinogen, SAA, NT-pro-BNP, change in hemoglobin and change in albumin from Baseline to End of Treatment (average of Week 10 and Week 12) between each active group and placebo.
- Difference in the percent change in TC, LDL-C, HDL-C, and TG from Baseline to End of Treatment (average of Week 10 and Week 12) between each active group and placebo.

2.3.3 Pharmacokinetic and Pharmacokinetic-pharmacodynamic Endpoints

The serum trough levels of Ziltivekimab will be measured at all visits, beginning with Visit 1.

The area under the curve for total IL-6 will be described.

The relationship between trough Ziltivekimab levels and PD parameters, specifically total plasma IL-6 and hs-CRP, will be described.

2.3.4 Safety Endpoints

The safety endpoints include the following:

- Description of safety assessments by treatment group and dose including adverse events (AEs), serious AEs (SAEs), vital signs, electrocardiogram (ECG) results, and clinical laboratory evaluations;
- Proportion of patients with AEs leading to discontinuation;
- Description and frequency of AEs of special interest (AESIs) by treatment group. AESIs include:
 - Serious infections
 - Common Terminology Criteria for Adverse Events (CTCAE) Grade ≥ 3 injection-related reactions
 - Gastrointestinal perforations
 - CTCAE Grade ≥ 3 anaphylaxis occurring at any time, even if considered unrelated to the study drug.
 - Neutrophil $< 500/\text{mm}^3$ (CTCAE Grade 4) or neutrophil $< 1000/\text{mm}^3$ (CTCAE Grade 3) with evidence of concurrent infection. These events will be separately summarized by treatment group and dose.
 - Thrombocytopenia (platelet count $< 50,000/\text{mm}^3$ [CTCAE Grade 3]) or platelet count $< 75,000/\text{mm}^3$ (CTCAE Grade 2) with evidence of concurrent major bleeding as defined by the Thrombolysis in Myocardial Infarction (TIMI) bleeding classification. These events will be separately summarized by treatment group and dose
 - Malignancies
- Description of anti-drug antibodies (ADAs) (binding and neutralizing).

3 STATISTICAL METHODOLOGY

3.1 General Considerations

3.1.1 Analysis Day

Analysis day will be calculated from the date of first dose of study drug. The day of the first dose of study drug will be Day 1, and the day immediately before Day 1 will be Day -1. There will be no Day 0.

3.1.2 Analysis Visits

Scheduled visits will be assigned to analysis visits as recorded in the electronic data capture (EDC) system. If a scheduled visit is not available, unscheduled and early termination visits will be assigned to analysis visits using analysis visit windows based on the actual date the assessment took place. The low analysis day of the analysis window will be calculated as the midpoint between the scheduled assessment and previously scheduled assessment for that parameter. The high analysis day of the analysis window will be calculated as the midpoint between the scheduled assessment and the next scheduled assessment for that parameter. Where multiple measurements for a particular parameter appear within an analysis window, the scheduled visit will be used. If no scheduled visit appears in the analysis window, the result closest to the target day will be used. If equidistant and both are unscheduled and/or early

termination visits, the later result will be used for the summary measure. For applicable efficacy parameters, “End of Treatment” visit will be derived where the average of assessments at Week 10 and Week 12 visits from the EDC will be calculated. Otherwise Week 12 visit will be used as the derived “End of Treatment” visit.

Analysis Visit	Target Analysis Day	Low Analysis Day	High Analysis Day
Baseline	1		1
Week 1	8	2	12
Week 2	15	13	19
Week 3	22	20	26
Week 4	29	27	36
Week 6	43	37	50
Week 8	57	51	64
Week 10	71	65	78
Week 12	85	79	92
End of Treatment	78	65	92
Week 16	113	93	133
Week 20	141	134	148

The observational period for the study will start from informed consent and end with study completion. Any event occurring after the defined observational period, even if collected on the case report form (CRF), may not be included in the planned statistical analyses. However, all data, including that reported after the defined observational period, will be included in the patient data listings.

3.1.3 Definition of Baseline

The Baseline value for hs-CRP level will be the average of all hs-CRP values prior to the administration of study drug. The Baseline value of other measures is defined as the last measurement collected prior to the administration of study drug, unless otherwise specified.

3.1.4 Summary Statistics

All study-collected data will be summarized by treatment group for the appropriate analysis population using descriptive statistics, graphs, and/or raw data listings. Descriptive statistics for continuous variables will include number of patients (with non-missing values), mean, standard deviation (SD), median, first and third quartiles, minimum and maximum values for the observed value, and change from Baseline. Analysis of categorical variables will include frequency and percentage. The denominator used for the percentage calculation will be clearly defined.

3.1.5 Handling of Dropouts and Missing Data

Missing data will be imputed only in the context of sensitivity analysis as described in section 3.4.1.

3.2 Analysis Populations

3.2.1 Intent-to-Treat (ITT) Population

The ITT Population is defined as all randomized subjects and will be the primary population for analysis of efficacy data.

3.2.2 *Per-Protocol (PP) Population*

The PP population will be the secondary population for analyses of disposition, baseline data, and efficacy data. For PP population, treatment classification will be based on the randomized treatment. The PP Population is defined as all subjects in the ITT Population who completed the study and did not incur a significant protocol violation that may impact the primary efficacy assessment. Significant protocol violations may include but are not limited to:

- Failed to meet eligibility criteria
- Took the wrong study drug (i.e., did not take the randomized study drug)
- Took a restricted concomitant medication
- Failed to complete the primary efficacy assessment

A list of subjects with significant protocol violations leading to exclusion from the PP Population will be finalized prior to unblinding the randomized treatment assignments.

3.2.3 *Pharmacokinetics (PK) Population*

The PK Population is defined as all randomized subjects who receive at least one dose of study drug and have at least 1 post-dose PK serum concentration. For the PK population, treatment classification will be based on the actual treatment received.

3.2.4 *Safety Population*

The Safety Population is defined as all randomized subjects who receive at least one dose of study drug. All safety data will be analyzed using the Safety Population. For the Safety population, treatment classification will be based on the actual treatment received.

3.3 Subject Data and Study Conduct

3.3.1 *Subject Disposition*

Counts and percentages of subjects who were randomized, discontinued early from the study, and completed the study will be summarized by treatment and in total based on all randomized subjects (ITT population). Reasons for early discontinuation will also be summarized.

3.3.2 *Protocol Deviations*

Protocol deviations are defined in the Protocol Deviation Plan and classified as CSR reportable or non-CSR reportable. All protocol deviations will be listed by deviation categories.

3.3.3 *Analysis Populations*

Counts and percentages of subjects in each analysis population will be summarized by treatment and in total based on all randomized subjects.

3.3.4 *Demographic and Baseline Characteristics*

The following demographic and baseline characteristics will be summarized:

- Age (years)
- Sex
- Race

- Ethnicity
- Height (cm)
- Weight (kg)
- Body mass index (BMI) (kg/m^2) and BMI categories ($<30 \text{ kg/m}^2$, $\geq 30 \text{ kg/m}^2$)
- CKD Stage (Stage 3, Stage 4 or Stage 5) as per randomization strata

Demographic and baseline characteristics will be summarized with descriptive statistics or counts and percentages of subjects as appropriate by treatment and in total for the ITT, per-protocol, and safety populations.

3.3.5 Medical History

Medical history will be coded to system organ class and preferred term using the Medical Dictionary for Regulatory Activities (MedDRA) version 21.0. Counts and percentages of subjects with medical history by system organ class and preferred term will be summarized by treatment and in total based on the ITT population.

3.3.6 Prior and Concomitant Medications

Prior and concomitant medications will be coded to anatomical therapeutic chemical (ATC) class and preferred term using the WHO Drug Dictionary. For summary purposes, medications will be considered prior medications if they were given before the first dose of study drug and concomitant medications if they were taken before and were continuing after the first dose of study drug or initiated after the first dose of study drug.

If a medication has incomplete start or stop dates, dates will be imputed to determine whether a medication should be considered prior or concomitant. If a medication start date is incomplete, the first day of the month will be imputed for missing day and January will be imputed for missing month. If a medication stop date is incomplete, the last day of the month will be imputed for missing day and December will be imputed for missing month. Incomplete start and stop dates will be listed as collected without imputation.

Counts and percentages of subjects taking prior and concomitant medications by ATC class and preferred term will be summarized by treatment and in total based on the Safety Population. Patients will be counted only once by medication class or name.

3.3.7 Study Drug Exposure

Weeks of exposure to study drug will be calculated as: $(\text{date of last dose of study drug} - \text{date of first dose of study drug} + 29)/7$. Note that the exposure calculation is intended to describe the length of time a subject was exposed to study drug and therefore does not take study drug interruptions into account. Weeks of exposure to study drug will be summarized by treatment based on the Safety population with descriptive statistics.

Study drug is planned to be administered every 28 days for a total of 3 treatments on Day1, Weeks 4 and 8.

Counts and percentages of number of injections received (1 to 3) with summary statistics will be summarized by treatment based on the Safety population. Number of subjects with injections at each visit will also be summarized along with the primary reason for injection not administered.

3.4 Efficacy (Pharmacodynamic) Assessment

For all continuous efficacy variables, the number of patients (n), mean, standard deviation (SD), median, quartiles (Q1 and Q3), minimum (min) and maximum (max) values for the observed value, change from baseline, and percent change from baseline will be reported on the ITT population. The difference (Ziltivekimab - Placebo) in percent changes will be presented. For categorical efficacy variables, the number of patients and percentage will be reported on the ITT population.

Due to the known distribution of the primary and secondary efficacy endpoints, normality assumption is usually difficult to satisfy; therefore, a non-parametric approach will be used for the primary and secondary efficacy analysis. Efficacy analysis will be carried out using the Hodges-Lehmann method to estimate median differences and its corresponding 95% confidence intervals for percent change from baseline to end of treatment between each treatment arm vs. Placebo, where end of treatment is the average of assessments at Week 10 and Week 12. The p-value from the Wilcoxon test will also be presented. The nonparametric analysis will account for the covariate CKD Stage (3 vs. 4 and 5) by aligning responses within the strata defined by the covariate prior to analysis.

Sensitivity analyses will be conducted to explore the robustness of the result for primary efficacy endpoint based on mixed models for repeated measures (MMRM) analysis using log of ratio to baseline, and multiple imputation analysis on a log scale. Sensitivity analysis will also be performed based on the PP population using the non-parametric approach. Efficacy data will be summarized by randomized treatment group based on the ITT and PP populations.

The differences in proportions and 95% CIs will be based on the normal approximation to binomials.

Missing data will be imputed only in the context of sensitivity analysis as described in section 3.4.1.

The pharmacodynamic efficacy of two Ziltivekimab doses compared to placebo will be assessed by evaluating the following:

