1.4.2. Phase 1 Study in Patients With Chronic Kidney Disease (COR-001-SC1)

[figure not shown]
This study was a Phase 1, randomized, double-blind, placebo-controlled, cohort dose-escalation study in patients with CKD to assess the safety, PK, and pharmacodynamics (PD) of a single dose of Ziltivekimab. The study population had moderate-to-severe CKD (ie, eGFR 20 to 60 mL/min/1.73 m²) who had serum CRP levels >2 mg/L over 2 consecutive measurements. The primary objective evaluated the safety of single SC doses of Ziltivekimab (planned doses of 5, 15, 50, and 100 mg). The main secondary objective evaluated single-dose PK of SC Ziltivekimab and the effects of Ziltivekimab on CRP and serum amyloid A (SAA).

After SC administration, Ziltivekimab concentrations reached peak levels by 7 to 17 days after dosing, on average, and serum Ziltivekimab concentrations remained quantifiable up to 217 days

postdose in all patients. Ziltivekimab concentrations increased in a dose-dependent manner. Terminal slopes (half-life) appeared similar for the 5 and 15 mg doses, suggesting linear PK. High intersubject variability among the 3 patients in the highest dose cohort (50 mg) confounded the interpretation for that dose. One patient in the 50 mg dose cohort had levels 2- to 3-fold higher than the other 2 patients so that it appeared that the latter patients displayed a less than dose proportional increase, while the former showed a greater than dose proportional increase in Ziltivekimab serum levels.

Mean hs-CRP levels were comparable and elevated at Baseline across placebo and the Ziltivekimab treatment groups, suggesting systemic inflammation. Figure 2 presents the percentage of patients who achieved an hs-CRP level of <2.0 mg/L from Baseline to Week 32. A consistent decrease in hs-CRP levels was observed in the Ziltivekimab dose groups throughout the first 8 weeks post randomization, while levels in the placebo group increased over time.

Figure 1 Percentage of Chronic Kidney Disease Patients Treated With Ziltivekimab or Placebo Who Achieved a High-Sensitivity C-Reactive Protein Level of <2.0 mg/L From Baseline to Week 32

hs-CRP = high-sensitivity C-reactive protein.

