4. SELECTION AND WITHDRAWAL OF PATIENTS

4.1. Inclusion Criteria

After signing an ICF approved by the Institutional Review Board (IRB) or Independent Ethics Committee (IEC), in order to be eligible, potential patients must meet all of the following criteria:

1. Age ≥ 20 years at the time of signing the ICF;
2. Stage 3 to 5 NDD-CKD, ie, eGFR >10 and <60 mL/min/1.73 m² using the CKD-EPI (Chronic Kidney Disease Epidemiology Collaboration) creatinine equation;¹³
3. Serum hs-CRP level ≥ 2.0 mg/L measured during the Screening Period.

Note: Targeting patients with a history of advanced stage CKD, ASCVD, anemia, diabetic retinopathy, obesity, or elevated body mass index (BMI), and diabetes for Screening will help increase the chances of identifying patients with hs-CRP ≥ 2.0 mg/L;

4. The patient agrees to comply with the contraception and reproduction restrictions of the study as follows (Appendix C):
 - a. Women of childbearing potential must be using a method of contraception that is “highly effective” (ie, $<1\%$ failure rate) for at least 3 months following the last dose of study drug;
 - b. Postmenopausal women must have had no menstrual bleeding for at least 1 year before initial dosing and either be over the age of 60 years or have an elevated plasma follicle-stimulating hormone (FSH) level (ie, >40 mIU/mL) at Screening;
 - c. Women of childbearing potential must have a documented negative serum pregnancy test result at Screening.; and
 - d. All male patients, from the day of dosing until the final study visit, unless surgically sterile, must be willing to use a condom with a partner (male patients with partners of childbearing potential must be willing to use 2 effective methods of birth control, 1 should be condom with spermicide) to prevent pregnancy and drug exposure of a partner, and refrain from donating sperm or fathering a child; and
5. The patient must be willing and able to provide informed consent and abide all study requirements and restrictions.

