2.2 Study Design

2.2.1 Overview

This is a randomized, double-blind, placebo-controlled study designed to evaluate the efficacy, safety, and PK of Ziltivekimab at 2 dose levels (15 mg or 30 mg) compared to placebo in Japanese patients with Stage 3 to 5 NDD-CKD and evidence of inflammation.

The study will consist of 3 periods: a Screening Period, a Treatment Period, and a Safety Follow-Up Period. The total study duration for each patient will be approximately 6 months.

- Screening Period: up to 2 weeks (Days -14 through -1)
The Screening Period starts on the date of informed consent, and this date will also be the date of the Initial Screening Visit.

- Treatment Period: 12 weeks (Baseline [Day 1] through Week 12)
The Treatment Period starts with the administration of study drug/randomization (Day 1).
- Safety Follow-Up Period: 8 weeks (Weeks 12 through 20)
The Safety Follow-Up Period starts 12 weeks after randomization

Patients will undergo a Screening Period of up to 14 days, during which the inclusion and exclusion criteria will be evaluated. Patients who meet all inclusion criteria and no exclusion criteria will be randomized 1:1:1 to Ziltivekimab 15 mg, Ziltivekimab 30 mg, or placebo (12 patients per group) for a 12-week Treatment Period. Approximately 36 patients will be randomized. Patient randomization will be stratified by CKD stage (3, 4 and 5). There will be approximately 10 sites in Japan.

After the Screening Period, patients will be randomized on Day 1. Randomized patients will receive multiple doses of study drug, and the initial dose of study drug will be administered after all assessments are conducted. Patients will then be followed for efficacy and safety through Week 12 and followed for safety in the Safety Follow-Up Period from Weeks 12 through 20. The primary endpoint evaluation will take place at the End of Treatment (using the average of Week 10 and Week 12 assessments).

Patients will be carefully monitored for 1 to 2 hours at the site post every dosing.

The schedule of procedures can be found in Appendix A of the protocol version 1.3.

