3.4.2 Exploratory Efficacy Endpoints

The exploratory analysis variables measuring change or percent change (as applicable) from baseline to end of treatment will be summarized and analyzed in the same manner as the primary analysis variable (section [3.4.1](#)).

For the continuous efficacy variables, the observed values, change from baseline, and percent change from baseline (as applicable) will be summarized by treatment group using descriptive statistics using ITT population.

For binary endpoints (proportions), proportions of patients and 95% CI for proportions will be based on the normal approximation to binomials. The differences in proportions and 95% CIs for differences for each active group will also be presented.

The sample SAS code for normal approximation of binary endpoints and to calculate differences in proportions and 95% CIs can be found below:

```
*****;  
*Note: ACHIEVE = status of patients achieving endpoint (1 if Yes, 2 if No)  
* TRT = Treatment Group  
*****;  
proc freq data=endpoint;  
by TRT;  
tables ACHIEVE / binomial (Wald exact);  
ods output BinomialCLs=CL BinomialProp=Proportion;  
  
run;  
  
proc freq data=endpoint (where=(trtpn in (#,#));  
table trt*RESPONSE / riskdiff;  
output out=proportion_diff RDIF2 ;  
  
run;
```

The following exploratory efficacy endpoints will be analyzed:

- Difference in the proportion of patients achieving hs-CRP response, defined as hs-CRP < 2.0 mg/L, at End of Treatment (average of Week 10 and Week 12) between each active group and placebo.
- Difference in the percent change in fibrinogen, SAA, NT-pro-BNP, change in hemoglobin and change in albumin from Baseline to End of Treatment (average of Week 10 and Week 12) between each active group and placebo.

- Difference in the percent change in TC, LDL-C, HDL-C, and TG from Baseline to End of Treatment (average of Week 10 and Week 12) between each active group and placebo.

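### The exploratory difference in hs-CRP response gets a Wald 95% interval with 12 patients per arm and no rule for sparse counts, so its precision can be overstated

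*SAP*

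**What the plan says.** SAP 3.4 sets the method for differences: "The differences in proportions and 95% CIs will be based on the normal approximation to binomials". SAP 3.4.2 says the same of the single-arm figures: "proportions of patients and 95% CI for proportions will be based on the normal approximation to binomials". The endpoint concerned is "Difference in the proportion of patients achieving hs-CRP response, defined as hs-CRP < 2.0 mg/L, at End of Treatment", where End of Treatment is the mean of the Week 10 and Week 12 values.

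The sample code in 3.4.2 has two parts. For each arm separately it asks for both kinds of limits: "tables ACHIEVE / binomial (Wald exact". For the difference it has only "table trt*RESPONSE / riskdiff", with no option naming a score, exact or corrected interval, which fits the normal approximation in the text. No alternative is given for small or boundary counts.

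The arms are small. SAP 2.2.1 has patients "randomized 1:1:1 to Ziltivekimab 15 mg, Ziltivekimab 30 mg, or placebo (12 patients per group". SAP 3.1.5 and 3.4 allow imputation only in the sensitivity analyses of the primary endpoint, so the evaluable number for this endpoint may be below 12.

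**The concern.** The Wald interval for a difference uses the observed proportions to estimate its own standard error. When an observed proportion is 0 or 1, that arm contributes no variance, and with 12 patients per arm such counts can occur. The interval is then too short, or of zero width. Being symmetric and unbounded, it can also run past 100%.

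The design makes such counts plausible, though not certain. Response uses the same cut-off as entry (Protocol 4.1: "Serum hs-CRP level ≥ 2.0 mg/L measured during the Screening Period"). In the earlier single-dose CKD study hs-CRP fell on active drug "while levels in the placebo group increased over time" (Protocol 1.4.2). The cut-off also matters for interpretation: Protocol 1.1.3 and 1.1.4 use it to connect biomarker response with fewer cardiovascular events. An interval of 100% to 100% from 24 patients would misstate what the trial had shown on that scale.

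There is also an inconsistency within SAP 3.4. It drops normality for the continuous endpoints as hard to satisfy, then relies on it for proportions out of 12.

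**Working it through.** **Inputs.** n = 12 per arm (SAP 2.2.1); Wald method (SAP 3.4 and 3.4.2); response is hs-CRP below 2.0 mg/L. The documents give no response rate and no power or precision figure for this endpoint, so there is no plan figure to reproduce; SAP 2.2.4 concerns the continuous primary endpoint. The rates below are therefore assumptions.

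**Step 1: the interval for particular counts.** With a and b the observed proportions on active and placebo:

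Wald limits = (a − b) ± 1.96 × √[a(1 − a)/12 + b(1 − b)/12]

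- 12/12 v 0/12: the difference is 1 and the root is 0, so the limits are 100% to 100%.
- 11/12 v 0/12: 0.917 ± 1.96 × √(0.917 × 0.083/12) = 0.917 ± 1.96 × 0.080, which is 76% to 107%.
- 10/12 v 1/12: 0.750 ± 1.96 × √(0.01157 + 0.00637) = 0.750 ± 1.96 × 0.134, which is 49% to 101%.
- 9/12 v 1/12: 38% to 96%, so no limit above 100%.
- 0/12 v 0/12: 0% to 0%.

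The Miettinen-Nurminen limits invert the score test with the variance taken at the restricted maximum-likelihood rates, multiplied by 24/23. For the same counts they are 71% to 100%, 61% to 99%, 37% to 91% (37.5% to 91.5%), 29% to 87%, and −25% to 25%. This step needs no assumption about true rates.

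**Step 2: how often it matters.** For each assumed pair of true rates, all 13 × 13 = 169 outcomes were weighted by their binomial probabilities. Coverage is the total probability of outcomes whose interval contains the true difference. The chance of zero width comes almost wholly from 12/12 v 0/12, so it is close to (active rate)^12 × (1 − placebo rate)^12; for 0.95 v 0.02 this is 0.95^12 × 0.98^12 = 0.42.

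| Active v placebo (assumed) | Wald coverage | Score coverage | Zero width | Upper limit above 100% |
|---|---|---|---|---|
| 0.95 v 0.02 | 57.5% | 95% | 42% | 55% |
| 0.95 v 0.05 | 70.5% | 97% | 29% | 66% |
| 0.90 v 0.05 | 84.0% | 97% | 15% | 70% |
| 0.90 v 0.10 | 91.3% | 97% | 8% | 66% |
| 0.80 v 0.10 | 88.5% | 95–96% | 2% | 41% |
| 0.80 v 0.20 | 87.1% | 93% | 0.5% | 23% |
| 0.70 v 0.20 | 92.0% | 95% | 0.1% | 9% |
| 0.60 v 0.20 | 93.5% | 95% | under 0.1% | 3% |

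Wald is below 95% in every row. The shortfall is severe only in the top three rows; elsewhere it is about 1.5 to 8 points. Zero width is a material risk only from about 0.90 v 0.10 outward. Impossible upper limits persist at milder rates.

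**Step 3: the Newcombe interval.** It also keeps non-zero width and stays within bounds for the counts in step 1 (12/12 v 0/12: 66% to 100%). Its coverage is lower near the boundary, for example 90.3% at 0.95 v 0.05.

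**The case against.** The best case against this point concerns premise and weight.

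First, a reader might infer that response rates will be near 0 on placebo and near 1 on active drug, so that a collapsed interval is to be expected. The documents do not establish that. Protocol 6.2.1 calls for a retest of screening values from 1.5 to just under 2 mg/L, there is no minimum at Day 1, and Baseline averages all predose values. Some patients can therefore start close to or below the cut-off, and regression to the mean could produce placebo responders. The rise on placebo in the earlier study points the other way, so the placebo rate is simply unknown. On active drug the only number is the planning difference of −60.74%. If a patient's own fall were that size, a baseline above 2.0/(1 − 0.6074) = 5.1 mg/L would still end above 2.0, and no baseline distribution is given. The rates must stay assumptions, and the milder rows belong in the table.

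Second, no decision depends on the interval. The endpoint is exploratory, the sequential test covers only the primary endpoint, and no test of proportions is specified. In the four rows 0.95 v 0.02, 0.95 v 0.05, 0.90 v 0.05 and 0.80 v 0.10, the Wald and score intervals disagree on excluding zero with probability of at most about 0.1%. Counts and percentages are reported as well, so a reader could spot the artefact.

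Third, the code already requests exact limits for each arm, so only the 3.4.2 sentence is out of step there.

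All three narrow the point. None supports a Wald interval for the difference at this sample size.

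**Conclusion.** The point holds for the between-arm difference. As written, the SAP gives a nominal 95% interval whose coverage at 12 per arm is 57.5% to 93.5% over the assumed rates, against 93% to 97% for a score interval. The interval can have zero width if rates are near 0 and 1, and it exceeds 100% in about 41% of trials at 0.80 v 0.10. These figures assume 12 evaluable patients per arm, independent binomial outcomes and the stated rates, none of which come from trial data.

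A reader might go further and conclude that the trial's evidence of efficacy is compromised. It is not: the primary analysis is a Wilcoxon and Hodges-Lehmann comparison of percent change and does not use this interval. What suffers is the stated precision of one exploratory result. The correction is worth making before database lock because it is cheap, but it is a minor one.

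**What to change.** - In SAP 3.4, replace the sentence on differences with a named score-type interval for the between-arm difference. Miettinen-Nurminen is the safer choice near the boundary; Newcombe would also remove the zero-width and above-100% results found here.
- In SAP 3.4.2, add the matching confidence-limit option to the riskdiff request and make sure those limits, not the default ones, reach the reported output. The SAP allows SAS 9.3 or higher, so confirm that the release in use offers the option.
- In SAP 3.4.2, reword the sentence on single-arm proportions so that the exact limits already requested in the code are the ones reported.

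The cost is a code option, two SAP sentences and generally wider intervals. No new data are needed, and the primary analysis and alpha control are untouched.
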